QCA and IVUS results from baseline, post procedure and 2 year are available for the patients in Cohort B Group 1. The 2-year angiographic results from Cohort B Group 1 demonstrated a late loss of 0.27 mm which compares well to the SPIRIT II XIENCE V 2 year late loss of 0.33 mm. Furthermore, in Cohort B Group 1 (n=33) IVUS data demonstrated lumen, scaffold and vessel enlargement between 6 months and 2 years (**Table 2.3**).

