#### ***5.2 Powered Secondary Endpoint(s)***

##### **Imaging Cohort Powered Secondary Endpoints**

Imaging Cohort Powered Secondary Endpoints are based on the pooled subjects from the Imaging Cohort of Absorb III (~ 200 angiographic subjects and ~150 IVUS subjects) and subjects from the Absorb Japan RCT (~ 400 angiographic subjects, and ~150 IVUS subjects).

One of the key attributes that differentiates Absorb BVS from metallic stents is the progressive mechanical weakening of the scaffold with polymer degradation over time, which allowed for vessel movement and gradual outward remodeling (positive) to accommodate any increases in the in-scaffold intimal hyperplasia that may limit blood flow. In both the Absorb Cohort A and Cohort B trials, Absorb BVS treated vessels have shown evidence of vessel movement and late lumen and scaffold enlargement, providing anatomic indication that the vessel can adapt and enable the natural Glagov process.

The vasomotion endpoint assesses the ability of the in-scaffold segment to move when the vessel is no longer mechanically constrained. Angiography will be used for the vasomotion assessment. The assessment of late lumen enlargement will be evaluated by the in-stent/scaffold mean lumen area change ( $\Delta$ MLA) from post-procedure to 3 years by IVUS.

1. The in-stent/scaffold mean lumen area change, from post-procedure to 3 years by IVUS (mean lumen area measured after nitrate infusions, superiority test, ~300 pooled subjects).
2. The in-stent/scaffold mean lumen diameter change, between pre- and post-nitrate infusion at 3 years by angiography (superiority test, ~600 pooled subjects).

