### **5.3 Additional Secondary Endpoint(s)**

In ABSORB III the following clinical secondary endpoints will be analyzed. Secondary imaging endpoints will be analyzed in the Imaging Cohort.

- **Acute Success:** (Combined Clinical/Angiographic Endpoint)
  - Device success (Lesion level analysis)
  - Procedural success (Subject level analysis)
- **Clinical Endpoint** in hospital and at each follow-up point (30 days; 180 days; 1, 2, 3, 4 and 5 years).
  - **Component**
    - Death (Cardiac, Vascular, Non-cardiovascular)
    - Myocardial Infarction
      - Attributable to target vessel (TV-MI)
      - Not attributable to target vessel (NTV-MI)
    - Target Lesion Revascularization (TLR)
      - Ischemia driven TLR (ID-TLR)
      - Non ID TLR (NID-TLR)
    - Target Vessel Revascularization (TVR,
      - ID TVR
      - Non ID TVR
    - All coronary revascularization
  - **Composite Endpoints**
    - Death/All MI
    - Cardiac Death/All MI
    - Cardiac Death/TV-MI/ID-TLR (TLF)

- Cardiac Death/All MI/ID-TLR (MACE)
- Cardiac Death/All MI/ID-TLR/ID-TVR, non TL (Target Vessel Failure, TVF)
- Death/All MI/All revascularization
- **Scaffold-Thrombosis / Stent Thrombosis (per ARC definition)**
  - Timing (acute, sub-acute, late and very late)
  - Evidence (Definite and Probable)
- **Imaging Endpoints:**

Imaging endpoints will be analyzed on Imaging Cohort subjects only.

○ **Angiography:**

All angiographic endpoints will be collected post-procedure and at 3 years

- In-segment late loss (LL)
- In-device LL
- Proximal LL (proximal defined as 5 mm of tissue proximal to the device placement)
- Distal LL (distal defined as 5 mm of tissue distal to the device placement)
- In-device/in-segment/proximal/distal minimum lumen diameter
- In-device/in-segment/proximal/distal %Diameter Stenosis (DS)
- In-device/in-segment/proximal/distal angiographic binary restenosis
- In-device net gain (change in minimum lumen diameter between 3 years and post-procedure)
- The magnitude of in-stent/scaffold mean lumen diameter change (absolute value) at 3-years follow-up from pre-nitrate to post-nitrate
- The normalized in-stent/scaffold mean lumen diameter change at 3-years follow-up from pre-nitrate to post-nitrate, defined as,

$$\frac{\text{In - Stent/Scaffold Mean Lumen Diameter change}}{(\text{Proximal Mean Lumen Diameter change} + \text{Distal Mean Lumen Diameter change})/2} \times 100\%$$

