 In-device refers to the margins of the stent or scaffold. Segment refers to the margins of the stent or scaffold and 5 mm proximal and 5 mm distal to the stent or scaffold.

 Device throughout the protocol summary refers to XIENCE or Absorb BVS System

Confidential and Proprietary

Do not distribute or reproduce without the prior written permission of Abbott Vascular Inc.  
ABSORB III Randomized Control Trial Version 17.0 August 16, 2018.

where both proximal and distal mean lumen diameter changes are at 3-years follow-up from pre-nitrate to post-nitrate

- Change in minimum lumen diameter, within treated segment, at 3 years follow-up from pre-nitrate to post-nitrate
- Change in in-device %DS at 3 years follow-up from pre-nitrate to post-nitrate

- **IVUS (Grey scale):**

All IVUS endpoints will be collected post-procedure and at 3 years (as applicable) and within the device and within the treated segment:

- Minimal Lumen Area
- Percentage of subjects with late gain without incomplete apposition by IVUS (IVUS minimum lumen area post- procedure post-nitrate - IVUS minimum lumen area 3 years follow-up post-nitrate)
- % change in the tissue area/volume between lumen and external elastic lamina (EEL)
- Absolute change in tissue area/volume between lumen and EEL
- Mean/minimal vessel diameter/area/volume
- Mean/minimal device diameter/area/volume; if analyzable in respect to Absorb BVS
- Mean/minimal lumen diameter/area/volume, including change in minimum lumen area between post-procedure and follow-up
- Mean/maximal neointima hyperplasia area/volume/percentage at 3 years; if analyzable in respect to Absorb BVS
- Incomplete apposition (post-implantation), persisting incomplete apposition, late acquired incomplete apposition and resolved incomplete apposition at 3 years; if analyzable in respect to Absorb BVS

- **OCT:**

All OCT endpoints will be collected post-procedure and 3 years, and for within the device and within the treated segment:

- Descriptive analysis of strut, lesion and vessel morphology
- Mean neointimal area (NIA)
  - Apposed to the vessel wall with neointimal coverage
  - Apposed to vessel wall without neointimal coverage

- Incomplete apposition to vessel wall with neointimal coverage
- Incomplete apposition to vessel wall without neointimal coverage
- Lumen area/volume stenosis %
- Mean/minimal device area
- Mean/minimal luminal area/volume
- Mean strut area/volume

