#### **Imaging Cohort Powered Secondary Endpoint 1**

The in-stent/scaffold mean lumen area change ( $\Delta$ MLA) from post-procedure to 3 years by IVUS (mean lumen area is to be measured after nitrate infusions) will be evaluated using the difference between the two means of the two treatment arms in the pooled subjects from the Imaging Cohort of ABSORB III and ABSORB Japan. Superiority testing will be performed with a two-sided alpha of 0.05. The null ( $H_0$ ) and alternative ( $H_A$ ) hypotheses for the superiority test are:

$$H_0: \Delta\text{MLA}_{\text{Absorb}} - \Delta\text{MLA}_{\text{XIENCE}} = 0$$

$$H_A: \Delta\text{MLA}_{\text{Absorb}} - \Delta\text{MLA}_{\text{XIENCE}} \neq 0.$$

$\Delta\text{MLA}_{\text{Absorb}}$  and  $\Delta\text{MLA}_{\text{XIENCE}}$  are the in-stent/scaffold mean lumen area changes in the Absorb BVS and XIENCE arms, respectively.

The sample size calculation is based on the following assumptions:

- The in-stent/scaffold mean lumen area change at 3 years for the Absorb BVS arm is assumed to be  $0.5 \pm 1.69 \text{ mm}^2$
- The in-stent/scaffold mean lumen area change at 3 years for the XIENCE arm is assumed to be  $-0.4 \pm 1.17 \text{ mm}^2$
- Two-sided alpha= 0.05
- $\sim 150$  subjects from the Imaging Cohort in ABSORB III, 50% IVUS follow-up rate at 3 years

- ~150 subjects from ABSORB Japan, 70% IVUS follow-up rate at 3 years
- ~15% of all subjects will have dual target lesion treatment.

An effective sample size of 207 lesions (138 for the Absorb BVS arm and 69 for the XIENCE arm) will provide approximately 99.4% power using two sample t-test.

The sample size calculation was performed using NCSS PASS 2008 (Hintze JL, 2002. PASS User's Guide-II. NCSS).

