## LATE LOSS (LL)

General definition: Calculated as MLD post-procedure – MLD at follow-up

- In-segment Late Loss: in-segment MLD post-procedure – in segment MLD at follow-up
- Proximal Late Loss: proximal MLD post-procedure – proximal MLD at follow-up (proximal defined as within 5 mm of healthy tissue proximal to the device placement)
- Distal Late Loss: distal MLD post-procedure – distal MLD at follow-up (distal defined as within 5 mm of healthy tissue distal to the device placement)
- In-device Late Loss: in-device MLD post-procedure – in-device MLD at follow-up

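### ABSORB III 5.3: the formula printed for the descriptive IVUS late-gain endpoint runs in the late-loss direction, and no cut-off for gain is given

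*Combined protocol and SAP*

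**What the plan says.** The IVUS list in ABSORB III section 5.3 includes the endpoint "Percentage of subjects with late gain without incomplete apposition by IVUS". The bracket that follows reads "IVUS minimum lumen area post- procedure post-nitrate - IVUS minimum lumen area 3 years follow-up post-nitrate". Neither the section nor the rest of the document supplied gives a threshold for late gain or says that a negative difference counts as gain.

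Three other places in the protocol bear on direction:

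- Appendix II, under late loss: "General definition: Calculated as MLD post-procedure – MLD at follow-up".
- Section 5.2, on the powered imaging endpoints: "The assessment of late lumen enlargement will be evaluated by the in-stent/scaffold mean lumen area change", taken from post-procedure to 3 years. Section 10.3.2 assumes this change is +0.5 (SD 1.69) mm² for Absorb BVS and -0.4 (SD 1.17) mm² for XIENCE.
- The angiographic list in section 5.3: "In-device net gain (change in minimum lumen diameter between 3 years and post-procedure". It names the two time points without writing out a subtraction.

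Sections 10.4 and 10.4.3 make the secondary endpoints outside the powered set descriptive and refer further detail to the SAP. No SAP text on this endpoint is in the document supplied.

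**The concern.** The label and the formula point in opposite directions. A subject whose minimum lumen area falls between the procedure and 3 years gets a positive value, and a subject whose lumen enlarges gets a negative one. Because the bracket is the only operational definition printed, a programmer who follows it and takes gain to mean a positive value would count narrowing as gain.

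What is at stake is one subject-level description of late lumen behaviour in the Imaging Cohort. If the sign is reversed, that percentage would favour the arm with more narrowing, and it would sit beside a powered lumen-area endpoint on which enlargement is positive.

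**Working it through.** **1. Sign of the printed formula.** Let A0 be the minimum lumen area post-procedure and A3 the minimum lumen area at 3 years, both post-nitrate. The bracket gives D = A0 − A3. If the lumen shrinks, A3 < A0 and D > 0. If it enlarges, A3 > A0 and D < 0.

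**2. Direction used elsewhere in the protocol.**

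| Place | Quantity | Order | A positive value means |
|---|---|---|---|
| 5.3, IVUS late gain | Minimum lumen area | Post-procedure minus 3 years | Smaller lumen |
| Appendix II, late loss | Minimum lumen diameter | Post-procedure minus follow-up | Smaller lumen |
| 5.2 and 10.3.2, powered IVUS endpoint | Mean lumen area | Change from post-procedure to 3 years | Larger lumen |

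The late-gain line therefore matches the definition of loss and opposes the endpoint chosen to measure enlargement.

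**3. Check against data that the protocol itself calls enlargement.** For Cohort B Group 1, section 2.1.9 says that "IVUS data demonstrated lumen, scaffold and vessel enlargement between 6 months and 2 years". Table 2.3 gives average lumen area as 6.36 mm² at 6 months and 6.85 mm² at 2 years. Earlier minus later is 6.36 − 6.85 = −0.49. From post-procedure (6.53 mm²) to 2 years it is 6.53 − 6.85 = −0.32. With gain read as a positive value, neither rise would count.

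**4. Check of the planning inputs.** The late-gain endpoint has no stated sample size, power or alpha, so it has no figure of its own to reproduce. The neighbouring powered endpoint does: "An effective sample size of 207 lesions (138 for the Absorb BVS arm and 69 for the XIENCE arm) will provide approximately 99.4% power".

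- Effective lesions: (150 × 0.50 + 150 × 0.70) × 1.15 = 180 × 1.15 = 207.
- Difference: 0.5 − (−0.4) = 0.9 mm².
- Standard error: √(1.69²/138 + 1.17²/69) = 0.201.
- Power: Φ(0.9/0.201 − 1.96) = 0.994, with the standard error carried unrounded. An unequal-variance t calculation also gives 99.4%.

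The stated 99.4% is reproduced. This power does not depend on the direction of subtraction, so the reversal leaves it unchanged.

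**5. Illustration of a sign flip.** This step borrows the mean-area planning values from section 10.3.2, assumes normality, takes gain to mean a value above zero, and ignores the apposition condition.

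- 3 years minus post-procedure above zero: Absorb BVS Φ(0.5/1.69) = 61.6%; XIENCE Φ(−0.4/1.17) = 36.6%.
- Post-procedure minus 3 years above zero, as printed: Absorb BVS 100 − 61.6 = 38.4%; XIENCE 100 − 36.6 = 63.4%.

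The ordering of the arms reverses.

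**The case against.** The best defence is that the intended direction is clear from the word gain and from section 5.2. The bracket could be read as merely naming two measurements, with the hyphen as a separator, and no rule for classing a subject is printed. The second half of this stands: taking a positive value as gain is the natural reading, but it is not stated. It does not rescue the line. Appendix II sets out late loss in the same layout as a true subtraction. If the hyphen here is only a separator, the endpoint has no formula, direction or threshold and still needs rewriting.

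A second defence is that the same IVUS list reports the change in minimum lumen area separately, so a reversed percentage would visibly disagree with those tables. That makes detection likely but does not correct the definition. The SAP may already hold the right form, which cannot be confirmed from the document supplied.

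A reader might also draw three stronger conclusions, which the documents do not support:

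- **That the late lumen enlargement claim is at risk.** The Protocol Summary and Introduction tie that label claim to the powered imaging endpoints. The relevant one is mean lumen area change, whose sign is consistent. The late-gain line is a separate, unpowered endpoint on minimum lumen area.
- **That the formula reports the exact complement of the named endpoint.** The endpoint requires both late gain and no incomplete apposition. Subjects with incomplete apposition fall in neither the named group nor the reversed one.
- **That the percentages estimate the error for this endpoint.** They rest on mean area, not minimum area, and on lesions pooled with ABSORB Japan, whereas section 5.3 restricts its imaging endpoints to the Imaging Cohort.

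**Conclusion.** The point holds as a reversed formula in the definition of a descriptive endpoint, with a missing cut-off beside it. The subtraction order contradicts the endpoint's own label, matches the protocol's definition of late loss, and opposes the sign convention of the powered IVUS endpoint. Nothing in the document supplied corrects it.

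The consequence depends on gain being read as a positive value. On that reading, subjects with a smaller minimum lumen area at 3 years and no incomplete apposition would be classed as having late gain, and the arm comparison for this endpoint could reverse. No estimate of the size for this endpoint is available, because the protocol gives no planning values for minimum lumen area and no apposition rate. The percentages in the working show only what a sign flip does.

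The primary endpoint, the powered endpoints, the sample size and alpha are untouched. The correction should be made, but nothing about the trial's main conclusions turns on it.

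**What to change.** In the IVUS list of ABSORB III section 5.3:

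- Define the difference as minimum lumen area at 3 years minus minimum lumen area post-procedure, both post-nitrate. Write minimum in full, because Appendix I reserves the abbreviation MLA for mean lumen area.
- Have the sponsor state the cut-off for late gain. Above zero is one option; the choice is the sponsor's.
- Keep the condition of no incomplete apposition.
- Check the SAP and the analysis programs for the same reversal.

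The cost is one line of protocol text and a check of the matching SAP entry and code. Data collection, sample size, alpha and trial conduct do not change.

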## **5.4 Informational Endpoints (Patient Reported Outcomes)**

In the 2000 primary analysis subjects of ABSORB III the following Patient Reported Outcomes will be analyzed as informational endpoints.

- Overall Health Status in hospital (baseline) and at the specified follow-up contacts (30 days; 1, 2, 3 and 5 years) assessed using the EuroQoL 5D (EQ-5D)
- Disease-Specific Quality of Life in hospital (baseline) and at the specified follow-up contacts (30 days; 1, 2, 3 and 5 years) assessed using the Seattle Angina Questionnaire (SAQ)
- Dyspnea severity in hospital (baseline) and at the specified follow-up contacts (30 days; 1, 2 and 3 years) assessed using the Rose Dyspnea Scale (RDS)
- Anxiety in hospital (baseline) and at the specified follow-up contacts (30 days; 1, 2 and 3 years) assessed using the Generalized Anxiety Disorder scale (GAD-7)

# **6. SUBJECT SELECTION AND WITHDRAWAL**

## **6.1 Subject Population**

Subjects registered into this Clinical Investigation will be male and female subjects derived from the general interventional cardiology population. The Clinical Investigation will register approximately 2250 subjects, with a maximum of two *de novo* native coronary artery lesions in separate epicardial vessels, who meet all eligibility criteria, have provided written Informed Consent and have been registered in the trial.

## **6.2 Subject Screening and Informed Consent**

### **6.2.1 Subject Screening**

Subjects planned to be admitted for a percutaneous coronary artery revascularization procedure should be screened for Clinical Investigation eligibility by a member of the research team previously trained to the Clinical Investigation Plan.

Subjects that have signed an Informed Consent (Refer to **Appendix IV**, Enrollment and Registration Process) are considered enrolled in ASBORB III. Subjects who do not satisfy the general angiographic inclusion and exclusion criteria and/or have unsuccessful pre-dilatation and/or vessel sizing are considered screen failures and will not proceed further in the trial. These subjects will be entered into the eCRF screening log (as applicable; in addition, the reason for screen failure as well as supporting data will be entered into the log).

### **6.2.2 Informed Consent**

The Investigator or designee, who has been trained on the protocol, will explain the nature and scope of the trial, potential risks and benefits of participation, and answer questions for the subjects. All subjects (or legally authorized subjects' representatives, if applicable) must sign and date the Institutional Review Board (IRB) /Medical Ethics Committee (MEC) approved informed consent prior to any clinical trial/investigation-specific procedures. No patients belonging to a vulnerable population will be enrolled. Vulnerable population is defined as subject whose willingness to volunteer in a clinical investigation could be unduly influenced by the expectation, whether justified or not, of benefits associated with participation or of retaliatory response from senior members of a hierarchy in case of refusal to participate. Examples of populations which may contain vulnerable subjects include: Individuals with lack of or loss of autonomy due to immaturity or through mental disability, persons in nursing homes, children, impoverished persons, subjects in emergency situations, ethnic minority groups, homeless persons, nomads, refugees, and those incapable of giving informed consent. Other vulnerable subjects include, for example, members of a group with a hierarchical structure such as university students, subordinate hospital and laboratory personnel, employees of the sponsor, members of the armed forces, and persons kept in detention.

Obtaining of the consent, provision of a copy to the subject, along with the date must be documented in the subject's medical records. The informed consent form must be signed by an investigator or designate trained on the protocol. In addition, the signed informed consent must be kept in the subject's medical records/research chart and a copy must be given to the subject or the legally authorized representative.

In addition, an authorization for use and disclosure of the subjects' protected health information, in accordance with the Health Insurance Portability and Accountability Act (HIPAA), must be obtained from the subject or their legally authorized representative (US only).

For Live cases at congresses the patients need to sign a specific Live Case ICF, approved by the IRB/EC and by Abbott Vascular, as well as by the competent authorities (e.g., FDA), as applicable. The investigator must request Abbott Vascular approval prior to, performing a Live Case.

## 6.3 Eligibility Criteria

Eligibility criteria are the same for all subjects in ABSORB III, unless specified.

### 6.3.1 General Eligibility Criteria

Assessment for general eligibility criteria is based on the medical records of the site and interview with a candidate subject. Clinical and laboratory test of the eligibility assessment shall be per site standard of care. If some of these tests are not included in the site's standard tests, they must be done, but after written Informed Consent has been obtained. Subjects must meet ALL of the inclusion criteria to be considered for the clinical evaluation. If ANY of the exclusion criteria are met, the subject is excluded from the clinical evaluation and cannot be registered.

#### 6.3.1.1 General Inclusion Criteria

1. Subject must be at least 18 years of age.
2. Subject or a legally authorized representative must provide written Informed Consent prior to any study related procedure, per site requirements.
3. Subject must have evidence of myocardial ischemia (e.g., stable, unstable angina, post-infarct angina or silent ischemia) suitable for elective PCI. Subjects with stable angina or silent ischemia and < 70% diameter stenosis must have objective sign of ischemia as determined by one of the following, echocardiogram, nuclear scan, ambulatory ECG or stress ECG). In the absence of noninvasive ischemia, FFR must be done and indicative of ischemia.
4. Subject must be an acceptable candidate for coronary artery bypass graft (CABG) surgery.
5. Female subject of childbearing potential who does not plan pregnancy for up to 1 year following the index procedure. For a female subject of childbearing potential a pregnancy test must be performed with negative results known within 7 days prior to the index procedure per site standard.
6. Female subject is not breast-feeding at the time of the screening visit and will not be breast-feeding for up to 1 year following the index procedure.
7. Subject agrees to not participate in any other investigational or invasive clinical study for a period of 1 year following the index procedure.

 This includes clinical trials of medications and invasive procedures. Questionnaire-based studies, or other studies that are non-invasive and do not require medication are allowed. A subject who is taking part in the long-term follow-up phase of a trial, who has completed all medications and invasive procedures per protocol requirements, may continue to participate in that trial.

